7.4.2.2 Primary Efficacy Endpoint evaluation in case of repeat assessments

The primary endpoint is defined as the time to first occurrence of disease reactivation during the RW phase. To distinguish between a disease reactivation and an appearance of clinical signs of an infection, the treating physician may decide to repeat clinical assessments within the protocol defined visit window. Those additional assessments are documented as a separate unscheduled visit in the database.

The handling of such repeat assessments is currently not described in the study protocol. If such repeat assessments are available, the evaluation of the treating physician whether clinical or laboratory signs of inflammation are considered as transient, infection-related manifestations or signs of a disease reactivation should be considered for the determination of a disease reactivation per protocol. This evaluation is done in a blinded manner prior to database lock and documented accordingly.

7.4.2.3 Sensitivity Analyses of the Primary Efficacy Endpoint

The primary endpoint analysis will be repeated on the RW-PPAS, provided the RW-FAS and RW-PPAS differ by at least one patient.

In addition, the following tipping point analyses will be performed for the primary endpoint to assess the impact of the different lengths of the RW phase due to the different versions of the protocol. For patients enrolled in protocol versions 4.0/4.1 and earlier whose planned RW duration was only 8 weeks and had no disease reactivation during the RW phase:

1. A worst-case imputation will be applied to patients in both treatment groups by assigning patients as having disease reactivation at the next day after the last per protocol visit.
2. A best-case imputation will be applied to patients in both treatment groups by assigning patients as not having disease reactivation until Week 16 of the RW phase.
3. A worst-case imputation will be applied to patients in the TA treatment group and a best-case imputation will be applied to patients in the Placebo treatment group.

7.4.3 Key Secondary Efficacy Endpoint Analysis Methods

The key secondary efficacy endpoint is response to therapy (including complete response and partial response) in the SAOL phase from Week 10 onwards and observed at least 2 consecutive visits at least 2 weeks apart. Patients who do not achieve complete response or partial response at 2 consecutive visits at least 2 weeks apart at Week 10 onwards or drop out prior to Week 10 will be considered non-responders. Patients who respond to therapy in the SAOL phase with complete or partial response will be summarized by the number and percent of patients along with the associated 95% exact Clopper-Pearson CIs.

The estimand for this endpoint will be described as:

Population: All patients in the SAOL-FAS population

Endpoint: Responder or non-responder.

Intercurrent events:

- Discontinuation prior to Week 10: patients who discontinue prior to Week 10 will be assigned as non-responders.
- Rescue immunosuppression treatment: patients who receive rescue immunosuppression treatment and continue in the SAOL phase and satisfy the criteria of responder will be considered responders.

Population-level summary: Number and percentage of responders and 95% exact Clopper-Pearson CIs.

A sensitivity analysis will also be performed that only considers assessments up to the start day of the rescue immunosuppression treatment.

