Complete and partial response to therapy from week 10 onwards was added as new key secondary endpoint. The evidence provided in the open label part to control the disease after the patients have entered the study in a status of high inflammatory activity is a crucial part to provide evidence of the efficacy of Tadekinig alfa treatment. The 10-week time point to begin assessing the response to therapy was chosen based on the timeline for steroid discontinuation and the need for the residual effect of steroids to no longer be present. Per the protocol, patients may receive Tadekinig alfa in addition to standard of care systemic steroids. The steroids are tapered down by day 28 after study initiation. However, a patient may receive another 28 day cycle of steroids upon initial disease reactivation, which is expected to occur during or shortly after the first steroid tapering. This results in a total expected time of 8 weeks of steroid taper. If patients are not stabilized after the second steroid taper, they are expected to start rescue immunosuppression and discontinue study treatment. Therefore, at week 10, patients are expected to no longer require steroids and any residual effects will not be present.

A patient's or caregiver's qualitative evaluation of health status was added with protocol version 6. Given the heterogeneous patient population (age range, disease symptom and impacts) and regulatory concerns that generic validated quality of life questionnaires would not be fit-for-purpose for use in this trial to support regulatory decisions, a non-validated questionnaire specifically designed for this patient population and study design is used. It captures the patient's or caregiver's qualitative evaluation of health status similar to the physician global assessment (PGA), the severity of individual symptoms and the perceived change in symptoms at the end of the SAOL and RW phase.

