C) Patients with a disease reactivation during the tapering down of the SOC during the combined treatment in the SAOL Phase:

If after an initial improvement in response parameters, the patients show again signs of increasing inflammation (i.e. partial or full disease reactivation) during the tapering down of SOC while in combined treatment, another full cycle of extended SOC (4 weeks) in addition to the IMP, will be initiated at the original dose.

In the last cases (B or C), the Investigator may also decide to start rescue immunosuppression treatment, and in this case the patient should discontinue study treatment due to treatment failure.

Note to treatment failure:

Any patient starting rescue immunosuppression treatment or treated with new/ increased doses of Permitted Concomitant Treatments will be considered a treatment failure and will proceed to the study discontinuation/early termination procedures. Data related to response to the rescue treatment will be collected including all key efficacy and safety assessments.

It is recommended that patients suffering from severe CNS manifestations are put on rescue immunosuppression treatment.

Note to treatment of disease reactivations:

Patients that present a partial or full disease reactivation after previous response to SOC + TA in the SAOL phase can remain in the study, and receive another cycle of SOC in addition to the continuous TA treatment, if according to treating physician, the severity does not require rescue immunosuppression.

Patients that present a partial or full disease reactivation in the RW Phase before the 16-week treatment is completed will proceed to the End of Study Visit and complete the RW Phase.

Note - normal ranges for ferritin and CRP:

The normal ranges of ferritin and CRP differ per age and respective normal ranges per age at the central or local laboratory will be used as reference.

Data Safety Monitoring Board

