11.2.4 Concomitant Treatment

All concomitant medications (together with route of administration) and treatment initiated during the period of the study between screening and end of the study will be recorded in the concomitant treatment section of the eCRF.

Permitted Concomitant Treatments

Patients can maintain treatment with stable doses of Non-Steroidal anti-inflammatory Drugs (NSAIDs), cyclosporine, tacrolimus and IL-1 inhibitors (anakinra, canakinumab, or rilonacept, or others). Dose increments for the permitted co-medications or their introduction after the beginning of the study are not permitted and represent treatment failures and study early termination. For cyclosporine and sirolimus treatments, the physician may need to change the dose slightly to readjust serum levels. Dose adjustments for keeping stable serum levels is acceptable during the study. The weaning of permitted co-medications after the beginning of the study are permitted and are evaluated as additional parameter for response to therapy; the decision for weaning other immunosuppressive therapies other than the SOC steroids is at the discretion of the treating physician and should be based on the individual patient's disease status. If permitted co-medications are weaned off during the course of the study and the investigator decides to re-introduce them, they are permitted as long as the doses are the same or lower than the doses that were administered at study entry.

Unauthorized Concomitant Treatments

The study-assigned treatments (Tadekinig alfa or placebo as randomized, plus SOC) are, in addition to the permitted concomitant medications if prescribed by the treating physician, the only treatment allowed during the study treatment period.

The need to use rescue immunosuppression will be considered as treatment failure and the patient will discontinue study treatment.

They include cytoablative drugs as etoposide, cyclophosphamide, etc. Specific cell-depleting agents such as **alemtuzumab**, **rituximab**, **anti-thymocyte globulin**. **Immunosuppressive antimetabolites such as 6-mercaptopurine and azathioprine** and **mycophenolate mofetil** that inhibits the proliferation of immune cells. Other biologics different to IL-1 blockers will also be considered as rescue immunosuppression, i.e. anti-TNF antibodies, **tocilizumab**, **vedolizumab**.

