6.1.4 Additional Standard of Care Cycles or Rescue Immunosuppression

A) If no response after the first combined treatment course (SOC + IMP) at the initiation of the SAOL phase:

If patients do not respond to study treatment after the initial combined treatment course, they will be treated with rescue immunosuppression or with new/ increased doses of permitted concomitant treatments. These cases will be considered treatment failures during the SAOL phase and will exit the study.

B) Patients with a disease reactivation after having responded to therapy in the SAOL phase:

If patients show signs of systemic inflammatory reactivation (ie, partial or full disease reactivation) after having responded to therapy in the SAOL phase, they will receive another cycle of SOC in addition to the IMP.

C) Patients with a disease reactivation during the tapering down of SOC during the combined treatment in the SAOL phase:

If after an initial improvement in response parameters, the patients show signs of increasing inflammation (ie, partial or full disease reactivation) during the tapering down of SOC while in combined treatment, another full cycle of extended SOC (4 weeks) in addition to the IMP will be initiated at the original dose.

In the last cases (B or C), the Investigator may also decide to start rescue immunosuppression, and in this case, the patient should discontinue study treatment due to treatment failure.

Any patient starting rescue immunosuppression treatment will be considered a treatment failure and will proceed to the study discontinuation/early terminations procedures. Data related to response to the rescue treatment will be collected including all key efficacy and safety endpoints.

It is recommended that patients suffering from severe CNS manifestations are put on rescue immunosuppression treatment.

Patients that present a partial or full disease reactivation after previous response to SOC + TA in the SAOL can remain in the study and receive another cycle of SOC in addition to the continuous TA treatment if, according to the treating physician, the severity does not require rescue immunosuppression. Patients that present a partial or full disease reactivation in the RW Phase before the 16-week treatment is completed will proceed to the End of Study Visit and complete the RW Phase.

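### The main analysis of the key secondary endpoint counts responses reached on rescue immunosuppression, although the protocol and the SAP itself call those patients treatment failures; new or increased co-medication is cut in neither analysis

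*SAP*

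**What the plan says.** SAP 7.4.3 names two intercurrent events for the key secondary endpoint. For early discontinuation, "patients who discontinue prior to Week 10 will be assigned as non-responders". For rescue, "patients who receive rescue immunosuppression treatment and continue in the SAOL phase and satisfy the criteria of responder will be considered responders". One sensitivity analysis is planned, which "only considers assessments up to the start day of the rescue immunosuppression treatment".

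Elsewhere rescue is treated as failure:

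- SAP 6.1.4: "Any patient starting rescue immunosuppression treatment will be considered a treatment failure".
- Protocol 9.1: "Any patient starting rescue immunosuppression treatment or treated with new/ increased doses of Permitted Concomitant Treatments will be considered a treatment failure".
- Protocol 11.2.4: "The need to use rescue immunosuppression will be considered as treatment failure and the patient will discontinue study treatment".

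Protocol 11.2.4 gives the same status to changes in permitted co-medication: "Dose increments for the permitted co-medications or their introduction after the beginning of the study are not permitted and represent treatment failures". SAP 6.1.2 repeats this. SAP 7.7, which lists departures from the protocol, does not mention the rescue rule.

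**The concern.** Protocol 8.3.3 starts the assessment at Week 10 so that residual steroid effect has gone, and it treats open-label disease control as an essential part of the efficacy evidence. The key secondary rate summarises that evidence. A rule that accepts responses obtained on rescue drugs works against the reason for the Week 10 start. Protocol 11.2.4 counts cytoablative drugs, cell-depleting agents and biologics other than IL-1 blockers as rescue, and a patient given any of them is to stop Tadekinig alfa. With no concurrent control, nothing in the analysis would separate their effect from that of the study drug.

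The SAP is also uneven on this. Its primary estimand (SAP 7.4.2.1) uses assessments only up to the start day of rescue. The randomized withdrawal (RW) analyses of mAIDAI and PGA (SAP 7.4.4.4 and 7.4.4.5) do keep post-rescue data, but they compare with placebo.

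**Working it through.** The documents give no expected response rate, sample size or power for this endpoint, so there is no planned figure to reproduce. The check is whether the rules allow a rescued patient to be counted, and how much one such patient would weigh.

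**Can a rescued patient be counted?**

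1. *Follow-up.* SAP 6.1 and Protocol 20.1 keep rescued patients on scheduled efficacy visits. Protocol 9.1 and SAP 6.1.3 follow patients who stop treatment up to the End of Study visit. Post-rescue response data can therefore exist.
2. *Definition.* In SAP 6.4.1.2 the bar on starting or increasing other immunosuppression sits under complete response only. Partial response needs at least a 50% reduction in affected organ categories, plus either at least half of the raised markers reaching complete-response levels or withdrawal of baseline immunosuppression. A patient on new rescue drugs can meet this, and partial response counts for the endpoint.
3. *Timing.* Protocol 8.3.3 puts the end of two steroid tapers at 8 weeks and adds: "If patients are not stabilized after the second steroid taper, they are expected to start rescue immunosuppression and discontinue study treatment". The only scheduled SAOL visits from Week 10 are Weeks 12 and 18 (Protocol 14.6 and 14.7), so both would fall after that rescue.
4. *The Week 10 bullet.* It does not say whether discontinuing refers to treatment or to visits. If visits, the patient rescued at about Week 8 can be a responder. If treatment, that patient is a non-responder. Rescue from Week 10 onward is outside the bullet on either reading.
5. *Co-medication.* The main analysis has no cut, and the sensitivity analysis cuts at rescue only. Assessments after new or increased permitted co-medication count in both.

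**How much does one patient weigh?**

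Inputs:

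- At most 15 enrolled (SAP 6.1).
- Three patients entered under the original design (SAP 6.1.5). Those randomized to placebo there appear only in listings (SAP 7.1.6).
- Assuming 15 enrolled and 0 to 3 such placebo patients, N runs from 15 down to 12.

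Shift in the rate = 1/N:

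| N | Shift (percentage points) |
|---|---|
| 15 | 6.7 |
| 14 | 7.1 |
| 13 | 7.7 |
| 12 | 8.3 |

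The SAP reports exact Clopper-Pearson 95% limits. The lower limit for k responders out of N is the 0.025 quantile of Beta(k, N − k + 1). At N = 15, for assumed counts of 8 and 13 true responders:

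| True responders | Lower limit | With one post-rescue responder added | Shift (points) |
|---|---|---|---|
| 8/15 | 26.6% | 9/15: 32.3% | 5.7 |
| 13/15 | 59.5% | 14/15: 68.1% | 8.5 (before rounding) |

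**The case against.** The strongest reply is that the SAP already plans the cut at rescue as a sensitivity analysis. Both rates would be reported, the endpoint is untested and outside the hierarchy (SAP 7.7), and the order of two descriptive rates is a choice of estimand. On this view, treatment failure in SAP 6.1.4 is a label for study conduct. The endpoint list (SAP 6.4.1.2) uses the same term for a patient with at least one reactivation, and the response definitions do not refer to it.

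The reach is also limited:

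- Protocol 11.2.3 and 20.1 link dropout to a long treatment stop. On that usage the patient rescued at about Week 8 is already a non-responder.
- On scheduled visits, a patient not responding at Week 12 cannot qualify. That leaves rescue between Weeks 10 and 12 with response at both visits, or a Week 12 responder rescued later who still responds at Week 18. Unscheduled visits could add cases.
- Case A non-responders leave the study at about Week 4 and are non-responders already. Missing response data also count as non-response (SAP 7.4.5.2).
- The co-medication route needs a treatment change that the protocol prohibits, followed by two responding visits.

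These limits stand, and they make the affected group small and possibly empty. They do not remove the problem. SAP 7.4.3 itself provides for rescued patients who remain in the phase. The dropout wording does not reach rescue from Week 10 on and is not repeated in the SAP. The sensitivity analysis does nothing for co-medication. The two senses of treatment failure do not justify crediting a rescue-drug response to a drug the patient should have stopped, and the main result would still be the version that does so.

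**Conclusion.** The concern holds. The main key secondary rate can include responses obtained on rescue drugs or on new or increased co-medication, and for co-medication neither planned analysis removes them. Each such patient adds 6.7 to 8.3 points to the rate for N of 15 to 12. At N = 15 the exact lower limit rises by 5.7 to 8.5 points across the assumed 8 to 13 true responders.

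This rests on full enrolment of 15. The number of affected patients is not given, and the effect is zero if none meets the criteria at two consecutive visits from Week 10. The endpoint carries no hypothesis test and the RW comparison is unaffected. The change should be made because this rate summarises the uncontrolled evidence on which the protocol relies.

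**What to change.** Change SAP 7.4.3 only:

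1. Replace the rescue bullet in the main analysis with: *Assessments after the start day of rescue immunosuppression, or of a permitted co-medication newly introduced or raised above its study-entry dose, do not count towards response.*
2. Exempt dose changes made to hold serum levels and re-introduction at or below the entry dose (both allowed by Protocol 11.2.4), and the repeat glucocorticoid cycles allowed under cases B and C of SAP 6.1.4.
3. Keep the present rule, under which rescued patients can be responders, as the sensitivity analysis.
4. In the discontinuation bullet, specify discontinuation of study treatment before Week 10.

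The cost is text in one SAP section, with the main and sensitivity versions changing places. The protocol and study conduct do not change. No new data are needed: Protocol 9.1 collects start and stop times for rescue and other medications, and the complete response definition already requires starts and increases of other immunosuppression to be known. The downside is that the reported rate may be somewhat lower.

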7.4.4 Secondary and Additional Efficacy Endpoint Analysis Methods

Secondary endpoints collected during the RW phase will be summarized for the RW-FAS. Selected secondary endpoints will also be summarized for the RW-PPAS, provided the RW-FAS and RW-PPAS differ by at least one patient. Reference [Section 7.4.6.5](#) for detail on testing procedures for secondary endpoints (ie, multiplicity adjustments).

Secondary endpoints collected during the SAOL phase will be summarized for the SAOL-FAS.

7.4.4.1 Best Response to Therapy During SAOL

The number and percent of subjects in each response category will be summarized, including: complete response, partial response, disease improvement, and no improvement or not evaluated.

7.4.4.2 *Treatment Failures during RW*

Patients meeting the criteria for treatment failure during the RW phase will be summarized by the number and percent of patients in each treatment group. The estimated difference in percentages (TA – placebo) among treatment failures between treatment groups will be presented along with the associated 95% exact CI. The 95% CIs for difference in binomial proportions will be computed based on exact unconditional confidence limits using the score statistic. Treatment groups will be compared for response to therapy versus treatment failure using the Fisher's exact test.

The estimand for this secondary endpoint will be described as follows:

Population: All patients in the RW-FAS population.

Endpoint: Treatment failure (Yes/No).

Intercurrent events: All patients who experience disease reactivation during the RW phase will be counted as treatment failure regardless of intercurrent events.

Population-level summary: Number and percentage of treatment failures, exact unconditional 95% CIs using the score statistic, and Fisher's exact test.

7.4.4.3 *Change from Baseline in C-reactive Protein and Serum Ferritin*

Descriptive statistics for the observed CRP and serum ferritin values and the changes from RW Baseline during the RW phase will be presented by visit for each treatment group. Descriptive statistics will include number of subjects, mean, standard deviation, 95% CI of the mean, median, Q1, Q3, minimum, and maximum values. Mean CRP and serum ferritin values with associated standard error bars will be plotted by treatment group over time during the RW phase. The primary comparison of change from RW Baseline values among treatment groups will be based on the Mann-Whitney-Wilcoxon test. As sensitivity analyses, the mean change from RW baseline will also be compared among treatment groups using Welch's two-sample test that allows for unequal variances, as well as by a linear regression model with Huber-white sandwich errors allowing for heteroscedasticity.

To assess the impact of possible variability in RW Baseline measures between groups, a rank analysis of covariance (ANCOVA) model with covariate adjustment for RW Baseline will be performed as a sensitivity analysis. This will be performed at all post-baseline visits during the RW phase that include a sufficient number of patients within each treatment group to allow for appropriate model testing. Model estimates for the linear regression model and the rank ANCOVA model will be presented to include the estimate of mean treatment difference, associated standard error, 95% CI of the mean difference, and p-value.

Descriptive statistics for the observed CRP and serum ferritin values and changes from baseline during the SAOL phase will be presented by visit.

7.4.4.4 *Modified Auto-Inflammatory Disease Activity Index*

Descriptive statistics for the mAIDAI total score (including both objective and subjective components) and changes from RW Baseline during the RW phase will be presented by visit for each treatment group. Descriptive statistics will include number of subjects, mean, standard deviation, 95% CI of the mean, median, Q1, Q3, minimum, and maximum values. Mean mAIDAI total score with associated standard error bars will be plotted by treatment group over time during the RW phase.

The primary comparison for the change from baseline in the mAIDAI total score among treatment groups will be based on the Mann-Whitney-Wilcoxon test.

The estimand for the secondary endpoint of change in mAIDAI total score from RW baseline to Week 34/ET will be described as follows:

Population: All patients in the RW-FAS population.

Endpoint: Change from RW baseline to Week 34.

Intercurrent events:

- Discontinuation prior to Week 34: change from baseline at Week 34 for patients who discontinue prior to Week 34 or for patients who were enrolled under protocol v4.0/4.1 and earlier and complete RW at Week 26 will be imputed using last observation carried forward (LOCF).
- Rescue immunosuppression treatment: patients who receive rescue immunosuppression treatment and continue in the RW phase will include all data captured within the RW phase including visits after receiving rescue immunosuppression treatment.

Population-level summary: Descriptive statistics and Mann-Whitney-Wilcoxon test.

As sensitivity analyses, change from baseline to maximum post-baseline score and change from baseline to last RW assessment up to the start day of rescue immunosuppression treatment will be summarized and compared among treatment groups. In addition, the mean change from RW baseline in the mAIDAI total score will also be compared among treatment groups using Welch's two-sample t-test that allows for unequal variances, as well as by a linear regression model with Huber-white sandwich errors allowing for heteroscedasticity. A rank ANCOVA model to include a covariate for the RW Baseline score will also be performed as sensitivity analysis, similar to the analysis of CRP and serum ferritin changes from RW Baseline. Model estimates for the linear regression model and the rank ANCOVA model will be presented to include the estimate of mean treatment difference, associated standard error, 95% CI of the mean difference, and p-value.

Shifts in mAIDAI responses from RW Baseline to each post-baseline visit during the RW phase will be summarized by component and treatment group (ie, present or absent at

baseline to present or absent at each post-baseline visit). Summarization will include the total counts for all responses reported at both RW Baseline and each post-baseline visit. Percentages will be based on the number of patients with a non-missing RW Baseline and non-missing post-baseline assessment at each visit.

The number and percent of patients who improve within each component (objective and subjective) of the mAIDAI will be summarized during the RW phase by visit and treatment group. For each component, only the number of patients who reported the assessment as present (1 or 2) will be considered for analysis. The proportion of patients who report the assessment as absent (0, ie, improved relative to baseline) at each post-baseline visit during the RW phase will be compared among treatment groups using the Fisher's exact test. Patients with a missing assessment at a post-baseline visit will be considered to have not improved.

Descriptive statistics for the mAIDAI total score and changes from baseline during the SAOL phase will be presented by visit. Shifts in mAIDAI responses from baseline during the SAOL phase will be presented by visit. The number and percent of patients who improve within each component of the mAIDAI during the SAOL phase will be presented by visit.

7.4.4.5 *Physician's Global Assessment*

Descriptive statistics for the PGA symptom severity score and changes from RW Baseline during the RW phase will be presented by visit for each treatment group. Descriptive statistics will include number of subjects, mean, standard deviation, 95% CI of the mean, median, Q1, Q3, minimum, and maximum values. Mean PGA symptom scores with associated standard error bars will be plotted by treatment group over time during the RW phase.

The primary comparison of the change from RW Baseline in the PGA symptom severity score among treatment groups will be based on the Mann-Whitney-Wilcoxon test.

The estimand for the secondary endpoint of change in PGA symptom severity score from RW baseline to Week 34/ET will be described as follows:

Population: All patients in the RW-FAS population.

Endpoint: Change from RW baseline to Week 34.

Intercurrent events:

- Discontinuation prior to Week 34: change from baseline at Week 34 for patients who discontinue prior to Week 34 or for patients who were enrolled under protocol v4.0/4.1 and earlier and complete RW at Week 26 will be imputed using LOCF.
- Rescue immunosuppression treatment: patients who receive rescue immunosuppression treatment and continue in the RW phase will include all

data captured within the RW phase including visits after receiving rescue immunosuppression treatment.

Population-level summary: Descriptive statistics and Mann-Whitney-Wilcoxon test.

As sensitivity analyses, change from RW baseline to maximum post-baseline score and change from baseline to last RW assessment up to the start day of rescue immunosuppression treatment will be summarized and compared among treatment groups. In addition, the mean change from RW baseline in PGA symptom severity score will also be compared among treatment groups using Welch's two-sample t-test that allows for unequal variances, as well as by a linear regression model with Huber-white sandwich errors allowing for heteroscedasticity. A rank ANCOVA model to include a covariate for the RW Baseline score will also be performed as sensitivity analysis, similar to the analysis of CRP and serum ferritin changes from RW Baseline. Model estimates for the linear regression model and the rank ANCOVA model will be presented to include the estimate of mean treatment difference, associated standard error, 95% CI of the mean difference, and p-value.

Shifts in PGA for stability of the patient's disease-related (auto-inflammatory) symptoms over the previous two weeks at RW Baseline to each post-baseline visit will be summarized by group (ie, improved, stable or worse at baseline to improved, stable, or worse at each post-baseline visit). Summarization will include the total counts for all responses reported at both baseline and each post-baseline visit. Percentages will be based on the number of patients with a non-missing RW Baseline and non-missing post-baseline assessment at each visit.

Descriptive statistics for the PGA symptom severity score and changes from baseline during the SAOL phase will be presented by visit. Shifts in PGA for stability of the patient's disease-related (auto-inflammatory) symptoms during the SAOL phase will be presented by visit.

